5 TREATMENT OF PATIENTS

5.1 Overview

All patients enrolled in the study should receive care consistent with local standard of care. Patients with worsening respiratory failure should receive conservative intravenous fluid strategies such as FACTT LITE. All patients should receive pharmacological prophylaxis to prevent the development of venous thromboembolic disease. The type and dose of prophylaxis should be determined by local standard of care.

Patients enrolled in the study should receive dexamethasone, or equivalent dose of another corticosteroid, as standard of care. If patients are not receiving dexamethasone at the time of randomization into CARDEA, starting dexamethasone during the hospitalization should be considered. If the patient is already receiving dexamethasone at the time of randomization, dexamethasone should be continued on its established dosing schedule. The COVID-19 Treatment Guidelines Panel of the National Institutes of Health recommends using dexamethasone (at a dose of 6 mg per day, given orally or intravenously, for up to 10 days) in patients with COVID-19 who require supplemental oxygen. Before initiating dexamethasone, the potential risks and benefits of administering corticosteroids should be assessed including risks for hyperglycemia and secondary infections. At this time, it is not known whether other corticosteroids, such as prednisone, methylprednisolone, or hydrocortisone, will have a similar benefit to dexamethasone. Of note, the dose equivalencies for dexamethasone 6 mg daily are prednisone 40 mg, methylprednisolone 32 mg, and hydrocortisone 160 mg.

If patients are not receiving remdesivir at the time of randomization into CARDEA, starting remdesivir during the hospitalization may be considered. If the patient is already receiving remdesivir at the time of randomization, remdesivir should be continued on its established dosing schedule. The suggested dose of remdesivir for adults weighing ≥40 kg and not requiring invasive mechanical ventilation and/or ECMO is a single dose of 200 mg infused intravenously over 30 to 120 minutes on Day 1 followed by once-daily maintenance doses of 100 mg infused intravenously over 30 to 120 minutes for 4 days (days 2 through 5). If a patient does not demonstrate clinical improvement, treatment may be extended for up to 5 additional days (i.e., up to a total of 10 days). Auxora and remdesivir should not infuse at the same time but should be given sequentially in any order.

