8.1.4 Derived Variables

8.1.4.1 Definition(s) of Baseline(s)

Unless otherwise specified, the baseline values are the last available assessment before or at the SFISD. If multiple measurements are recorded on the same day, the last measurement recorded prior to the dose of study medication will be used as the baseline value. If these multiple measurements occur at the same time or time is not available, then the average of these measurements (for continuous data) or the worst among these measurements (for categorical data) will be considered as the baseline value. **Baseline imputed PaO₂/FiO₂ is the worst value in the 24 hours before screening.**

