8.4 Primary Endpoint Analysis

8.4.1 Definition of Endpoint

Time to recovery through the Day 60 visit in the 8-point ordinal scale is the primary endpoint.

The primary estimand corresponding to the primary endpoint is defined as:

1. Treatment: 2.0 mg/kg (1.25 mL/kg) of Auxora administered at 0 hour and 1.6 mg/kg (1 mL/kg) administered at both 24 hours and 48 hours from the Start of the First Infusion of Auxora with local standard of care.
2. Population: Severe COVID-19 pneumonia patients with a baseline imputed $\text{PaO}_2/\text{FiO}_2 \leq 200$.
3. Variable: Time to recovery defined as time from SFISD to the first time a patient achieves the scale of 6, 7 or 8 on the 8-point ordinal scale for at least 24 hours.
4. Population level summary: Median difference using Kaplan-Meier estimate

Intercurrent events under consideration: 1) prohibited immunosuppressive medications or immunotherapies. 2) convalescent plasma treatment, 3) treatment discontinuation and 4) death.

The null and alternative hypotheses are:

- Null hypothesis H_0 : Time to recovery curves are the same between the two treatment arms
- Alternative hypothesis H_1 : Time to recovery are different between the two treatment arms

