8.4.2 Main Analytical Approach

Time to recovery through Day 60 visit will be displayed using a Kaplan-Meier estimate and will be compared between the 2 treatment groups using stratified log-rank test stratified by baseline imputed $\text{PaO}_2/\text{FiO}_2$ screening of ≤ 100 vs. > 100 . Prohibited immunosuppressive medications or immunotherapies, convalescent plasma treatment and treatment discontinuation will be ignored (treatment policy strategy). Death will be treated as not recovered and time to recovery will be censored at Day 65 (composite strategy). Patients, including withdrawal of consent patients, will be censored at the last ordinal scale assessment if no recovery event is observed during the study (administrative censoring). The trial level Type I error of 0.05 between the two tests of the primary endpoint analysis and the key secondary endpoint analysis is controlled using the Benjamini and Hochberg method.

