8.8.2 Subgroup Analyses

Subgroup analyses will be performed to explore how time to recovery through Day 60 visit and mortality at Day 60 visit are influenced by baseline variables and to evaluate the treatment effect at different levels of each of these variables. The Kaplan-Meier analysis, Cox model and CMH test will be performed by subgroup levels of the baseline variables listed below:

- Age ($<65, \geq65$)
- Baseline CRF calculated imputed $\text{PaO}_2/\text{FiO}_2$ ($\leq100, 101-200, \geq201$)

- Race (White, Black, Asian, Other).
- Gender (Male, Female)
- BMI ($<30, \geq 30$)
- Remdesivir (being already administered at randomization, administration started after randomization, never administered)
- Dexamethasone (being already administered at randomization, administration started after randomization, never administered)
- Remdesivir and Dexamethasone (being already administered together at randomization or administered together starting after randomization)
- Convalescent plasma (being administered at randomization, administration started after randomization, never administered)

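### SAP 8.8.2 treats background treatments started after randomization as baseline subgroup levels, which builds immortal time into those tables

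*SAP*

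**What the plan says.** SAP 8.8.2 gives one of its aims as: "explore how time to recovery through Day 60 visit and mortality at Day 60 visit are influenced by baseline variables". The other aim is to see how Auxora performs within each level. It states the method as: "The Kaplan-Meier analysis, Cox model and CMH test will be performed by subgroup levels of the baseline variables listed below". The list includes "Remdesivir (being already administered at randomization, administration started after randomization, never administered". Dexamethasone and convalescent plasma have the same three-way split. The joint item reads "Remdesivir and Dexamethasone (being already administered together at randomization or administered together starting after randomization".

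Protocol 10.8.10 carries the same levels under the same baseline label, for time to recovery only. SAP 8.8.2 adds Day 60 mortality.

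Four other places bear on the point:

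- SAP 8.1.4.1: "Unless otherwise specified, the baseline values are the last available assessment before or at the SFISD".
- SAP 8.4.1: "Time to recovery defined as time from SFISD to the first time a patient achieves the scale of 6, 7 or 8".
- Protocol 5.1, for patients not on the drug at randomization: "starting remdesivir during the hospitalization may be considered". Dexamethasone has a parallel sentence.
- SAP 8.4.3 censors at convalescent plasma in one sensitivity analysis of the primary endpoint. It covers neither remdesivir nor dexamethasone and does not extend to the subgroups.

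**The concern.** Being on a drug at randomization is a legitimate baseline level. Starting it later, or never starting it, can be known only from follow-up, and the follow-up that decides the level is the same follow-up that yields the outcome.

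Recovery is timed from SFISD and includes every discharge. Remdesivir and dexamethasone starts happen in hospital. A patient who recovers quickly has little time to start and tends to be counted as *never*. A patient classed as *started after* is guaranteed to have been unrecovered up to the start. That guaranteed stretch is immortal time.

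Two readings of the tables are exposed:

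- How outcomes vary across levels, which is one of the two stated aims.
- The Auxora effect within each level, if Auxora changes how long patients remain able to start or changes the decision to start.

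Background treatment is prominent in protocol 5.1, so these rows will be read for consistency of the Auxora effect. A baseline label hides that two of the three levels are decided after randomization.

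**Working it through.** **The plan's figures.** SAP 8.8.2 states no number to reproduce. The design figures that supply the assumed Auxora effect do reproduce. With 1:1 allocation, two-sided 0.05 and 90% power, events = 4(1.960 + 1.282)² / (ln ratio)². Ratio 1.43 gives 42.03 / 0.1279 = 329, against 330 stated. Ratio 1.49 gives 42.03 / 0.1590 = 265, against 320 × (330/400) = 264.

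**Mechanism by hand.** Assume exponential recovery with a median of 10 days, so λ = ln 2 / 10 = 0.0693 per day and mean recovery is 14.4 days. The background drug is inert and starts at σ = 0.05 per day while the patient is unrecovered, with no cut-off.

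- Share that starts: σ/(λ+σ) = 0.05/0.1193 = 0.419.
- Mean recovery time in *never*: 1/(λ+σ) = 8.4 days.
- Mean recovery time in *started after*: 8.4 + 14.4 = 22.8 days, because after the start the remaining time is a fresh exponential.
- Check: 0.419 × 22.8 + 0.581 × 8.4 = 14.4.

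The drug does nothing, yet the levels differ by 14.4 days.

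**Restricted start windows.** Starts count only up to day W, where the share starting is [σ/(λ+σ)](1 − e^(−(λ+σ)W)). For W = 28 and σ = 0.05 this is 0.419 × 0.965 = 0.40. The longest window is 28 days because in-hospital concomitant-medication visits end there (protocol 8.10, Appendix 2). Simulations used 400,000 patients per scenario and follow-up to Day 60. Frailty, where used, is a log-normal multiplier (SD 1) on the recovery rate. All rates, windows and frailty settings are assumptions.

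Started-versus-never recovery ratio in the placebo arm (true value 1.0):

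| Start window | Starts independent of prognosis¹ | Start rate proportional to frailty² |
|---|---|---|
| 3 days | 0.84–0.91 | 1.37–1.55 |
| 5 days | 0.75–0.85 | 1.21–1.36 |
| 10 days | 0.57–0.74 | 1.04–1.09 |
| 28 days | 0.50–0.58 (half candidates), 0.27–0.40 (all) | 0.54–0.74 |

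¹ Starts 5–8% per day, 50–100% of patients candidates, with and without frailty. ² Better-prognosis patients start sooner; 5–20% per day; the 10- and 28-day rows take all patients as candidates.

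With a weaker link to prognosis (start rate proportional to the square root of frailty), the ratio is 1.13 at 3 days and 0.98–1.02 at 5 days.

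**Auxora versus placebo within levels**, true ratio 1.49, prognosis-independent starts at 5–8% per day:

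- 3- and 5-day windows: the two levels differ by at most 0.05, about simulation noise.
- 10-day window: at most 0.07.
- 28-day window, all candidates, no frailty: 1.57 in *started after* versus 1.33 in *never* (5% per day); 1.55 versus 1.28 (8%).
- 28-day window, all candidates, with frailty: 1.27 versus 1.25 and 1.26 versus 1.20, against 1.30 overall.
- Auxora affecting neither recovery nor starting: 0.99–1.01.
- Auxora halving starts without affecting recovery: 0.73–1.00 in *never*, 0.90–1.00 in *started after*.

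Faster starting brings the gap forward. At 20% per day, all candidates, no frailty, the same model gives 1.50 versus 1.34 for a 10-day window.

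**Mortality.** Under a constant death hazard (0.012 per day) without frailty, the levels have equal mortality (14–15%). A gap (21–24% versus 17–20%) appears only if death is assumed to be inversely tied to recovery frailty.

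**Alternatives.** With prognosis-independent starts, a time-dependent covariate returns 0.99–1.01 for the inert drug. In separate runs with a true Auxora ratio of 1.43, a Day 3 landmark returns between-level ratios of 1.00–1.01 and arm ratios of 1.42–1.44 within both levels.

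**The case against.** **Direction.** A reader might infer that the bias always makes *started after* look worse. The documents do not support that. Immortal time pushes that way, but selection can push back. Protocol 5.1 frames its suggested remdesivir dosing around patients not on invasive ventilation or ECMO, which could leave sicker patients in *never*. The right-hand column of the table shows the sign reversing for short windows. This objection stands.

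**False-positive rates.** It is tempting to attach an inflated type I error to these tables. SAP 8.8.2 specifies no test between levels; its analyses run by level. Any such rate would describe an unplanned test. It would also depend on how many patients were already on the drug, and protocol 5.1 makes corticosteroid treatment standard of care, so few may remain to start. No rate is claimed here.

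**The treatment comparison.** The main analysis "will be compared between the 2 treatment groups using stratified log-rank test", and the natural subgroup counterpart is Auxora versus placebo within level. At the assumed 5–8% per day that comparison is barely disturbed unless starts run well past Day 10. The scenario in which Auxora halves starting has no support in the documents for a double-blind trial. This also stands, subject to the faster-start result above.

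**Breach of the baseline definition.** SAP 8.1.4.1 allows exceptions, so this is a mislabel and not a formal violation.

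**Existing cover.** SAP 8.3.3 already summarizes newly started corticosteroids and antivirals by arm, and SAP 8.4.3 deals with plasma for the primary endpoint. Neither changes how the subgroups are defined.

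The analyses are exploratory. That lowers the stakes but does not make levels decided during follow-up interpretable as baseline.

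**Conclusion.** The concern holds as a labelling error with a structural consequence. Two of the three levels for each background treatment, and the second half of the joint item, are not baseline, and nothing in either document handles start time for these subgroups. Confidence is high on the label and on the presence of immortal time, and on nothing beyond that.

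The net direction and size are not determined. They rest on the timing of starts, the share of patients still able to start, and the link between starting and prognosis, none of which the documents give. The assumed scenarios span ratios from 0.27 to 1.55 where the truth is 1.0. A distortion of Day 60 mortality is not established; it appeared only under an added assumption.

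A reader might also infer that the trial's main conclusions are at risk. They are not: the primary and key secondary tests do not use these levels. The correction should be made, but it concerns interpretation of exploratory tables only.

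**What to change.** In SAP 8.8.2:

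- Define the remdesivir, dexamethasone and convalescent plasma subgroups by status at randomization only (already receiving: yes/no), and the joint item as both remdesivir and dexamethasone at randomization (yes/no).
- State how a start between randomization and SFISD is classed.
- Document the departure from protocol 10.8.10.
- Report later starts descriptively by arm. SAP 8.3.3 already does so for corticosteroids and antivirals; extend it to convalescent plasma, which protocol 8.13.1 requires to be recorded as a concomitant medication.
- If an effect of later starts is wanted, use a time-dependent covariate or a landmark, labelled as post-randomization and non-randomized. Either removes the immortal time but not confounding by prognosis.

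The cost is SAP wording and a documented departure. No new data are needed, and the only loss is the three-level tables. If the sponsor prefers to keep them, label the later levels as post-randomization and state that they are not for causal or between-level reading.

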9 INTERIM ANALYSIS

9.1 Interim Sample Size Re-estimation and Futility Analysis

One unblinded interim sample size re-estimation is planned and was conducted by the IDMC when 70 patients in the baseline imputed $\text{PaO}_2/\text{FiO}_2 \leq 200$ subgroup have completed the study.

In the protocol plan, the conduction power of the time to recovery will be calculated based on the conditional power analysis of the time to recovery by assuming the interim estimated parameter values as the estimates of these parameters. Sample size will be re-estimated at the interim analysis to provide a conditional power of 90%, based on the interim evaluation of the treatment efficacy. The study will use a sequential design with O'Brien-Fleming critical boundary (O'Brien and Fleming 1979) at the interim analysis to control type I error. In case of sample size modification, the final critical boundary will be adjusted to control type I error (Gao et al., 2008). Based on the estimated standard error of 0.25 from Part 1 data, the relationship between the observed recovery ratio at interim analysis and the re-estimated sample size to reach 90% conditional power is shown in the following table:

Table 4 Relationship Between the Observed Recovery Ratio at Interim Analysis and the Re-estimated Sample Size to Reach 90% Conditional Power

O'Brien-Fleming boundary at the interim analysis, interim analysis at information fractions 0.25, Standard error of log(recovery ratio) = 0.25				
Observed recovery ratio at interim analysis	Conditional power based on interim estimation	Sample size (events) to reach 90% conditional power based on interim estimation	Conditional power based on recovery ratio = 1.37	Sample size (events) to reach 90% conditional power on recovery ratio = 1.37
1.57	97%	214 (178)		
1.47	90%	290 (241)		

1.44	86%	320 (266)		
1.40	80%	384 (318)		
1.39	78%	400 (332)		
1.37	67%	438 (363)		
1.34	59%	500(415)		
1.31	59%	600(503)		
1.20	28%	1414(1174)	64%	507(421)
1.10	8%	5648(4688)	56%	563(468)
1.05			52.2%	596(495)
1.00			48%	630(523)

Based on the above relationship, the following sample size re-estimation rule is proposed for this study at the interim analysis of the 70 patients in the imputed $\text{PaO}_2/\text{FiO}_2 \leq 200$ subgroup:

- Recovery rate ratio <1.05 , increase sample size >600 for imputed $\text{PaO}_2/\text{FiO}_2 \leq 200$ subgroup
- Recovery rate ratio 1.05 to <1.34 , increase sample size to 600 for imputed $\text{PaO}_2/\text{FiO}_2 \leq 200$ subgroup
- Recovery rate ratio 1.34 to 1.38 , increase sample size to 500 for imputed $\text{PaO}_2/\text{FiO}_2 \leq 200$ subgroup
- Recovery rate ratio 1.39 to 1.43 , increase sample size to 400 for imputed $\text{PaO}_2/\text{FiO}_2 \leq 200$ subgroup
- Recovery rate ratio ≥ 1.44 , do not increase sample size for imputed $\text{PaO}_2/\text{FiO}_2 \leq 200$ subgroup

The sample size re-estimation rule was updated and a non-binding futility analysis was added prior to the conduct of the interim sample size re-estimation. The updated sample size re-estimation rule was based on the promising zone with re-estimated sample size of 500 patients. The study used a sequential design with O'Brien-Fleming critical boundary ([O'Brien and Fleming 1979](#)) at the interim analysis to control type I error. In case of sample size modification, the final critical boundary will be adjusted to control type I error ([Gao et al., 2008](#)). The detailed promising zone rule is described in the separate interim statistical analysis plan and was finalized before the interim sample size re-estimation.

9.1.1 Critical Boundary Adjustment

If the sample size is modified to a new information time T_{new} , the second critical boundary, $c_2 = 1.96$ will be modified according to [Gao et al., 2008](#):

$$C_{new} = \frac{1}{\sqrt{T_{new}}} \left\{ \frac{\sqrt{T_{new} - t_{interim}}}{\sqrt{T - t_{interim}}} (C_2 \sqrt{T} - s_{interim}) \right\} + \frac{s_{interim}}{\sqrt{T_{new}}}.$$

This adjustment properly controls the type I error.

10 VALIDATION

The tables, figures and listings (TFLs) planned in this SAP will be programmed using SAS software version 9.4 (or above). The TFLs will be quality checked by the statistics team at Princeton Pharmatech using SAS software version 9.4 (or above).

11 PROGRAMMING AND DATA PRESENTATION CONVENTIONS

Listings will be presented in treatment, subject, visit (where applicable) and date (where applicable) order. Listings will be produced (landscape in MS Word) using PROC REPORT.

Summary tabulations will be presented by treatment group (and overall if appropriate), scheduled visit order (if appropriate). Continuous data summaries will present (unless stated otherwise) number of observations, mean, standard deviation, median, minimum and maximum. Categorical data summaries will present the number of observations and the corresponding percentage.

